12.2.2 Planned statistical methods

All quantitative analyses will be done on Stata Version 17 (College Station TX: StataCorp LP). We will use paired sign-rank tests to compare continuous scores of stigmas and quality of life and Man-Whitney U tests for cross-sectional comparisons during follow up. Adherence (which is the primary efficacy variable) will be determined by comparing detectable ASM levels in blood against proportion of prescribed doses correctly taken, with a binary variable for adherence generated from established detectable and optimal levels of ASM in blood. Generalized estimating equations, with appropriate link functions (i.e. specifying binomial family and log link), will be used to analyse adherence binary status in panel data format, across the follow-up periods of baseline, 3 months, 6 months and 12 months. For cross-sectional evaluations at each follow-up period e.g. at 3 months, will be done using generalised linear models with appropriate link function (i.e. specifying binomial family and log link). Both generalised estimating equations and generalised linear models will produce Absolute relative risks (RR) which will be subtracted from one to compute efficacy (i.e. efficacy=1-

RR). We will conduct interim analysis at the halfway mark to assess performance of the intervention. For secondary efficacy variables, specifically stigma scores and quality of life scores, we will first generate discrete variables of improvement by subtracting baseline scores from follow up scores and repeat efficacy analysis using the approaches described for primary efficacy variable i.e., adherence. All levels of efficacy analysis will be done including Full Analysis Set (FAS), Intention-to-treat population (ITT), and Per Protocol population (PP). Multivariable logistic regression will be performed to investigate association between type and ASM blood levels and incidence of adverse events.

For qualitative studies, standard analysis approaches, will be used including transcribing verbatim, coming up with a preliminary thematic framework through reading a sample of the transcripts. The thematic framework will be used to create a coding structure in NVivo, the software that will be used for final analysis including inter-rater coding and data management/filing.

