We will send out reminders to some participants either as a text, a picture, or both a text and a picture to remind them to take their medication. In addition, we will also engage staff at peripheral health facilities where the PWE go for medication refills through ongoing capacity building of all healthcare providers in public health facilities in Kilifi County on management of epilepsy and direct engagement of the respective county Departments of Health to ensure sustained supply and availability of drugs for managing epilepsy. We will ask participants questions regarding how they take their medications, their quality of life and stigmatising experiences before and after they have received message reminders. These sessions will take about 3 hours, including breaks and time spent for clarification and obtaining samples. All study activities will take place at KWTRP in Kilifi and APHRC in Nairobi. Messages will be sent throughout the 12 months for each individual participant and assessment of adherence, quality of life and stigma will be done at the first visit and subsequent follow up visits at 3, 6 and 12 months into the study. To confirm self-reported adherence, we will also collect blood

samples of not more than 5 ml from participants and compare the concentration of antiseizure medications before and after they have received message reminders. Blood samples will be collected at the clinics during the first visit and subsequent follow up visits. All the samples will be stored at KWTRP Main Laboratory and analyses will be conducted at the end of the study at the CREATES Laboratory (<https://creates.strathmore.edu/>) hosted by Strathmore University. Clinicians attending to PWE in the study will continue to advice all participants on the need for adhering to their medication for good outcomes as part of routine care.

What are the benefits and risks/costs of the study for those involved?

Benefits:

If message reminders are found to be useful, they will help in improving adherence outcomes and quality of life among people with epilepsy while reducing misperceptions about epilepsy and stigma experienced by these people.

Risks:

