A multisite study in Africa showed that the burden of epilepsy in many rural parts of Africa is greater than elsewhere across the globe (Ibinda et al., 2017b). Recent pilot studies in Kilifi of epilepsy (both with convulsive and non-convulsive seizures) revealed a hidden burden of non-convulsive seizures (Kariuki et al., 2021), further widening the treatment gap for these people.

The pooled adherence treatment gap in Kilifi as measured by optimal drug levels has been reported as 79.1% (95% CI; 73.3 to 84.3%), with adherence based on blood levels being more reliable than self-reports using a locally validated and adapted Morisky Medication Adherence Scale (MMAS-8) (Ibinda et al., 2017b). An educational intervention in Kilifi, Kenya resulted in improved adherence in both arms (36% to 85% in cases and 38% to 74% in controls) probably due to sharing of learned information among participants or study staff offering psychosocial counselling to both groups (Ibinda et al., 2014). However, this intervention was costly to sustain and may not improve nonadherence due to forgetfulness associated with epilepsy-related intellectual disability (Mwangala et al., 2018).

Poor compliance has been identified in scientific studies as affecting the concentrations of these medications in blood. These varying concentrations in blood can then affect how a person responds to treatment or whether they experience drug-related side effects including symptoms of psychosis (Chen et al., 2012), weak bones (Zhang et al., 2020) or enlarged gums (Silvado et al., 2018). Other people with epilepsy may also fail to take their medications correctly because of side effects caused by their medications which may discourage compliance. Therefore, we can plan to document drug-related toxicities as reported by patients and in relation to plasma ASM levels.

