12.0 STATISTICS

12.1 Determination of sample size

The minimum sample size determination will be based on reducing the adherence treatment gap from the current estimates of 62% in Kilifi ((Ibinda et al., 2017a) aiming for a proportion of improvement of 40%-50%. Previous studies have shown non-adherence of >60% even among clinic attendants, especially when symptoms subside. Assuming a refusal/non-consent/attrition rate of 10% and design effect of 1.5 (assuming possibility of modest clustering), if we recruit 300 patients at each arm, i.e., total of 1200 patients, we will have 95% power to detect a 50% improvement in adherence. Therefore 1,200 PWE will be randomized into 4 arms as follows: text SMS (N=300), graphic SMS (N=300), both text and graphic SMS (N=300) and control/non-reminder SMS (N=300). An allocation ratio of 1:1:1:1 across the 4 arms will be used. Since no prevalence estimates exist for the Nairobi site, we will utilise a similar sample size for each site. This sample size determination will account for these unprecedented withdrawals by recruiting a surplus of participants, assuming a proportion of 20% loss to follow up.

Table 2. Sample size adjusted for 10% attrition at varying improvements and powers

Improvement	Power			
	80%	90%	95%	
40%	588	786	971	
45%	268	358	442	
50%	154	205	253	

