16.4 Patient Data Protection/Confidentiality

Participants will be assured about confidentiality of the personal details obtained from them since seizure disorders are associated with stigma in most rural areas of Kenya (Mbuba et al., 2012b). We will deliberately explain to community members and PWE that epilepsy is not a

mental health disorder in all communications and that people with either conditions should not be stigmatised. Any clinical interviews will be carried out in private rooms. The messages will not have any personally identifiable information to ensure privacy of the participants. Caregivers/members of the household, especially those who receive messages on behalf of PWE will also be encouraged to handle the messages with confidentiality to prevent access of the messages by others outside the household which may lead to stigmatisation or breach of confidentiality. We are also running community awareness studies as part of the EPIInA studies to reduce the enacted and perceived stigma around epilepsy. All current COVID-19 mitigation protocols will be adhered to during clinic visits including wearing of masks, social distancing, sanitising and temperature checks in line with the Ministry of Health guidelines. Participants will be provided with contact details of investigators for any enquiries and clarifications.

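### For stigma and quality of life, the first-named test is a before-after test that cannot separate the messages from background change, and no baseline-adjusted reminder-versus-control contrast is made decisive

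*Combined protocol and SAP*

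**What the plan says.** Section 6.2 puts quality of life and stigma beside adherence in the primary objective. The synopsis and 10.1.2 list changes in both as secondary outcomes.

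For these scores, 12.2.2 opens: "We will use paired sign-rank tests to compare continuous scores of stigmas and quality of life". Section 12.2.1 says the same. The sentence goes on to Mann-Whitney tests for cross-sectional comparisons at follow-up. Later, 12.2.2 turns follow-up minus baseline into discrete improvement variables and repeats the relative-risk efficacy analysis on them. Neither section names a reference arm, a contrast between arms or an arm-by-time term, or says which of the three analyses carries the conclusion.

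For drug levels, the lay summary (section 2.0) plans to "compare the concentration of antiseizure medications before and after they have received message reminders".

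Several things act on all arms. From section 2.0: "Clinicians attending to PWE in the study will continue to advice all participants on the need for adhering to their medication". From section 16.4: "We are also running community awareness studies as part of the EPIInA studies to reduce the enacted and perceived stigma around epilepsy". Sections 1.4 and 8.5 describe supply work and provider training at facility level.

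Section 5.1 reports that an educational intervention in Kilifi "resulted in improved adherence in both arms (36% to 85% in cases and 38% to 74% in controls"), and explains the rise in both arms as "probably due to sharing of learned information among participants or study staff offering psychosocial counselling to both groups". Section 12.1 starts from a 62% adherence gap and states: "we will have 95% power to detect a 50% improvement in adherence".

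**The concern.** A paired test asks whether scores moved from baseline, not whether they moved more with reminders than without. Stigma is the direct target of the community programme, and quality of life could improve with better supply and closer follow-up. A significant paired test in a reminder arm would therefore be expected if the background work succeeds, whatever the messages do. If the report leads with that test, as the plan does, it could claim a message effect on two outcomes named in the primary objective without evidence for it.

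The history in section 5.1 also bears on section 12.1. Control adherence there did not stay at its starting level, yet the power statement makes no allowance for such a rise.

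**Working it through.** **A. Paired test versus between-arm test when the messages do nothing**

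Inputs: 300 per arm (12.1) and 20% loss (12.1), so 300 × 0.8 = 240 per arm. Assumed, because the documents give no figures: normally distributed scores, baseline-to-follow-up correlation r = 0.5, the same shift δ (in SD units) in both arms, and a two-sided 5% level.

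- SD of change = √(2(1 − r)) = √(2 × 0.5) = 1 SD.
- The signed-rank test has efficiency 3/π = 0.955 relative to the paired t test for normal data. Rejection probability ≈ Φ(δ√(240 × 0.955)/SD of change − 1.96), and √(240 × 0.955) = 15.14.
- At δ = 0.2: 0.2 × 15.14 = 3.03, and Φ(3.03 − 1.96) = Φ(1.07) = 0.86.

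| Shared shift (SD) | Signed-rank within one arm, formula | Same, simulated (2,000 runs) | Mann-Whitney between arms, simulated |
|---|---|---|---|
| 0.1 | 33% | 33–34% | 4–5% |
| 0.2 | 86% | 84–87% | 5–6% |
| 0.3 | 99.5% | 99.5% | 4–5% |

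The simulation was run twice; the ranges span both runs.

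Range over the assumed correlation at δ = 0.2:
- r = 0.2: SD of change = √1.6 = 1.265; 3.03/1.265 = 2.39; Φ(0.43) = 67%.
- r = 0.8: SD of change = √0.4 = 0.632; 3.03/0.632 = 4.79; Φ(2.83) = more than 99%.

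The between-arm test keeps its level because a shift common to both arms cancels.

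**B. What the 95% power depends on**

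*The plan's own figure.* Table 2 gives 253 per arm for 50% improvement at 95% power. The pooled two-proportion formula with 30% v 50% reproduces it:
- n = [1.96√(2 × 0.4 × 0.6) + 1.645√(0.3 × 0.7 + 0.5 × 0.5)]² / 0.2² = (1.358 + 1.116)² / 0.04 = 153.
- 153 × 1.5 (design effect) × 1.1 (attrition) = 252.

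The 30% is inferred and not printed. The stated 62% gap implies 100 − 62 = 38%.

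*Power at 300 per arm.* Effective n per arm is m = 300 × 0.9/1.5 = 180 at 10% attrition, or 300 × 0.8/1.5 = 160 at 20%; section 12.1 gives both attrition figures. Power = Φ(|p₁ − p₀| / √[(p₀(1 − p₀) + p₁(1 − p₁))/m] − 1.96), for one reminder arm against control at one site.

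- 38% v 57% (38 × 1.5 = 57): variance sum 0.2356 + 0.2451 = 0.4807. At m = 180: 0.19/0.0517 − 1.96 = 1.72, power 96%. At m = 160: 0.19/0.0548 − 1.96 = 1.51, power 93%.
- 74% v 85% (the earlier Kilifi endline): variance sum 0.1924 + 0.1275 = 0.3199. At m = 180: 0.11/0.0422 − 1.96 = 0.65, power 74%. At m = 160: 0.11/0.0447 − 1.96 = 0.50, power 69%.
- A 20-point gap held at control rates from 30% to 74%: power at least 95% throughout.

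**The case against.** The strongest reply is that the trial is randomised, with concurrent controls who get the same routine care plus messages unrelated to epilepsy. The sentence that names the paired test also names Mann-Whitney tests, and 12.2.2 adds a relative-risk analysis of improvement that uses each participant's baseline. Nothing declares the paired test to be the efficacy test, and most sections treat stigma and quality of life as secondary.

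Much of this stands. The design can remove background change, and the plan contains analyses that could use it. What remains is that the plan does not commit to them. Three analyses of the same scores are listed with none made decisive. The Mann-Whitney test ignores baseline, and discrete improvement discards information in the continuous score.

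Stronger readings that a reader might infer are not supported:

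- *Background change inflates the adherence result.* Adherence is analysed by GEE and GLM relative risks, not by a before-after test. Care common to randomised arms does not bias a between-arm relative risk towards the messages, and contamination would shrink it.
- *The lay summary makes before-after drug levels an efficacy test.* That wording appears only there, and it is introduced as a check on self-report.
- *Before-after analysis overstates the effect 3.8-fold.* The earlier trial gives 85 − 36 = 49, 74 − 38 = 36, 49 − 36 = 13 and 49/13 = 3.8. These are adherence percentages and do not measure inflation in stigma or quality of life.
- *A 50% improvement could not occur with controls at 74%.* That follows only if it means a relative rise in adherence (0.74 × 1.5 = 1.11). Section 12.1 speaks of reducing a gap, and halving a 26% gap gives 87%.
- *A higher control rate by itself destroys power.* The fall to 74%/69% comes from an 11-point effect borrowed from a different, educational intervention. With both sites pooled, which the plan does not state, power would be about 96%/93%.

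**Conclusion.** The point holds for stigma and quality of life. The first-named test answers the wrong question, and no baseline-adjusted between-arm comparison of the continuous scores is specified as the basis for conclusions. With a shared shift of 0.2 SD and no message effect, the paired test would be significant about 85% of the time (67% to over 99% for correlations of 0.2 to 0.8), against about 5% between arms. The shift and the correlation are assumptions; the documents report neither.

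The power point is separate and of lower priority. The 95% depends on the assumed control rate and effect size, and falls to about 74%/69% for the earlier Kilifi endline (one arm pair, one site, two-sided 5% assumed because 12.1 states no level). It is not a source of bias.

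This should be corrected before analysis, but it does not threaten the design or the between-arm adherence comparison.

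**What to change.** In 12.2.1 and 12.2.2, state that conclusions on stigma and quality of life rest on the concurrent reminder-versus-control difference in follow-up score, adjusted for the participant's baseline score, and name control as the reference arm. Keep paired signed-rank tests only as description of within-arm change. Label the before-after comparison of drug levels in section 2.0 the same way.

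In 12.1, state the control rate and effect behind the 95% and add a short table of power over control adherence from 38% to 74% and over plausible gaps, at 10% and 20% attrition.

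The cost is wording, a small table and a less favourable power statement in some scenarios. Baseline and follow-up scores are already collected, so no new data or participants are needed. The contrast should be fixed before outcome data are seen by arm, including at the interim analysis, since a choice made later would carry little weight.

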1.4 PROTOCOL SYNOPSIS

Full Title	Evaluation of a Mobile Messaging Service (Text and / or Graphic) in Improving Adherence with Ensured Supply of Anti-seizure Medications in People with Epilepsy in Kilifi and Nairobi, Kenya
Short Title	SMS Trial
Trial Phase	Not Applicable
Objectives	
Primary Objective: To examine the impact of sending text or graphic SMS reminders on anti-seizure medication (ASM) adherence people with epilepsy in Kilifi and Nairobi, Kenya
 
Secondary Objectives: To describe the perceptions and perspectives of people with epilepsy (PWE) and their caregivers on the use of text and graphic SMS reminders to improve adherence to anti-seizure medications (ASMs) among PWE in Kilifi and Nairobi, Kenya
 
To compare the effectiveness of text versus graphic messaging service in improving adherence in people with epilepsy in Kilifi and Nairobi, Kenya
 
To identify the factors associated with improvement in adherence, improved quality of life (QoL) and reduction in stigma-associated suffering among PWE and family members.
 
To document the common adverse drug reactions (ADRs) related to commonly prescribed ASMs and the plasma levels associated with these ADRs among PWE in Kilifi and Nairobi, Kenya
 
To evaluate the cost-effectiveness of the interventions in each of the sites

Trial Design	Partially-blinded randomized controlled trial
Sample Size	1200 participants (900 participants in the intervention arm (300 receiving text SMS, 300 receiving graphic SMS, 300 receiving both text and graphic) and 300 in the control arm/receiving non-reminder messages) in each site
Study Population	We will include participants who fulfil the following criteria:

	
 i. children or adults with a diagnosis of epilepsy ascertained by a clinician at the epilepsy clinic, taking anti-seizure medications at the time of the study, ii. persons living within an area defined as the Kilifi Health Demographic Surveillance System (KHDSS) or the Nairobi Urban Health Demographic Surveillance System (NUHDSS) at the time of the study, or attending the epilepsy clinics in Kilifi or the Kenya Association for the Welfare of persons with Epilepsy (KAWE) clinics in Nairobi iii. persons able to give written informed consent or assent (for children 13-17 years old) iv. persons with access to a basic mobile phone in the household either through direct ownership, a caregiver or a member of the household nominated by the PWE

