6.3 Secondary objective(s)

- (i) Using qualitative methods, to describe the perceptions and perspectives of PWE and their caregivers on the use of text and graphic SMS reminders to improve adherence to ASMs among PWE in Kilifi and Nairobi, Kenya
- (ii) To compare the effectiveness of text versus graphic messaging service or both in improving adherence among people with epilepsy in Kilifi and Nairobi, Kenya
- (iii) To identify the factors associated with an improvement in adherence and improved QoL among PWE and reduction in stigma among PWE and their family members.
- (iv) To document the adverse drug reactions (ADRs) including neurologic and psychiatric ADRs related to frequently prescribed ASMs types and, where possible, plasma levels among PWE in Kilifi and Nairobi, Kenya
- (v) To conduct cost-effectiveness analysis of rolling out the interventions among PWE in Kilifi and Nairobi, Kenya

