9.2.6. Procedures

(i) Clinical evaluation, assessment of stigma scores and measures of quality of life

During the baseline visit, information regarding epilepsy factors including seizure semiology, electroencephalography (EEG) and medical co-morbidities as well as sociodemographic characteristic will be assessed using tools that have been validated in this setting. Comprehensive clinical examination, and assessment of self-reported sigma and measures of quality of life and collection of blood samples will also be conducted at the baseline visit. Stigma scores will be assessed using standardized Kilifi Epilepsy Stigma Scale and while quality of life will be assessed using the World Health Organization Quality of Life Scale (WHOQOL-BREF). These tools will be validated for the Nairobi site prior to administration.

(ii) Measurement of adherence

Information on adherence to ASMs will also be collected using a validated self-reporting tool, the Morisky Medication Adherence Scale (MMAS-8) and validated using blood samples. Blood will be drawn (not exceeding 5mls) to measure detectable and optimal plasma levels of ASMs at baseline and during three follow up timepoints; at three months, six months and at 12 months (table 1). Optimal and detectable levels of ASMs in blood. All assays for ASMs will be done at the end of the study using a TDxFx analyser and automated VitaLab Selectra E Clinical Chemistry (Abbott Laboratories, Abbott Park, IL, USA) at Centre for Research in Therapeutic Sciences (CREATEs), Strathmore University.

(iii) Short message service (SMS) intervention

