10.1.2 Secondary efficacy variable(s)

- (i) Correct intake of drugs and refill rates- measured by checking record logs for participants attending the epilepsy clinics and identified in the surveys in NUHDSS
- (ii) Changes in seizure frequency as assessed by trained clinicians at the epilepsy clinics and identified in the surveys in NUHDSS
- (iii) Changes in stigma scores and quality of life scores assessed using standardized scales
- (iv) Unwanted drug-related adverse events as reported by participants and confirmed using standardized questionnaires.

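### One follow-up-minus-baseline rule defines improvement for both stigma and quality of life, although benefit is a fall on one and a rise on the other, so the signs of the two results can conflict

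*Combined protocol and SAP*

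**What the plan says.** Section 12.2.2 introduces the rule with "For secondary efficacy variables, specifically stigma scores and quality of life scores" and continues "we will first generate discrete variables of improvement by subtracting baseline scores from follow up scores and repeat efficacy analysis", by the approaches used for adherence. Those are generalised estimating equations across visits and generalised linear models at single visits, both with a binomial family and log link. They yield "Absolute relative risks (RR) which will be subtracted from one to compute efficacy".

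The intended direction of benefit appears elsewhere. Section 6.3 looks for factors associated with "improved QoL among PWE and reduction in stigma among PWE and their family members", and the synopsis has "improved quality of life (QoL) and reduction in stigma-associated suffering among PWE and family members". Section 10.1.2 is neutral: "Changes in stigma scores and quality of life scores assessed using standardized scales". Section 9.2.6 names the instruments ("Stigma scores will be assessed using standardized Kilifi Epilepsy Stigma Scale", and WHOQOL-BREF for QoL) but does not say which way either is scored.

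The same scores have a second planned analysis in Section 12.2.2: "We will use paired sign-rank tests to compare continuous scores of stigmas and quality of life", with Mann-Whitney tests for cross-sectional comparisons during follow-up. Section 6.2 lists both outcomes under the primary objective, while Section 10.1.2 classes them as secondary.

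**The concern.** A single subtraction is labelled improvement for two outcomes whose benefits run in opposite directions. Follow-up minus baseline is positive when a score rises. That suits a scale on which higher is better. It does not suit a stigma scale on which higher is worse, and no section reverses the sign for stigma. The result then goes to a binomial model, so it must be cut into yes and no, and the plan does not say where or in which direction.

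A programmer following the text could code a participant whose stigma fell as not improved. The stigma and QoL results would then disagree in sign for the same true benefit. The formula 1 − RR adds to the difficulty: it is natural for an unfavourable event, whereas improvement is a favourable one. This variable is the only planned route to a between-arm effect estimate for stigma and QoL, both of which Section 6.2 places under the primary objective.

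**Working it through.** The documents state no figure for this point, so there is none to reproduce. The check traces the sign of the derived variable and illustrates it numerically.

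**From Section 12.2.2**
- Difference D = follow-up score − baseline score, for both scales.
- RR = P(improved, intervention) / P(improved, control).
- Efficacy = 1 − RR.

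**Assumed, not in the documents**
- Higher score = more stigma; higher score = better QoL.
- Literal coding: improved means D > 0.
- D is normal with SD 1 and no ties. Its mean is 0 in control and is shifted by d in the beneficial direction under intervention, with d = 0.2, 0.3 or 0.5 SD.

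**Formulas** (Φ is the standard normal distribution function)
- Control: P(D > 0) = P(D < 0) = 0.50.
- Stigma, literal coding: mean of D is −d, so P(D > 0) = Φ(−d) and RR = Φ(−d) / 0.50.
- Stigma coded by its benefit (a fall = improved): P(D < 0) = Φ(d) and RR = Φ(d) / 0.50.
- QoL, literal coding: mean of D is +d, so RR = Φ(d) / 0.50.

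**At d = 0.3**
- Φ(−0.3) = 0.382, so literal stigma RR = 0.382 / 0.50 = 0.76 and 1 − RR = +0.24.
- Φ(0.3) = 0.618, so QoL RR = 0.618 / 0.50 = 1.24 and 1 − RR = −0.24.
- Stigma with a fall coded as improved also has RR 1.24 and 1 − RR = −0.24.

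**Over the range**

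| d (SD) | Stigma, literal: RR | 1 − RR | Stigma, fall = improved: RR | 1 − RR | QoL: RR | 1 − RR |
|---|---|---|---|---|---|---|
| 0.2 | 0.84 | +0.16 | 1.16 | −0.16 | 1.16 | −0.16 |
| 0.3 | 0.76 | +0.24 | 1.24 | −0.24 | 1.24 | −0.24 |
| 0.5 | 0.62 | +0.38 | 1.38 | −0.38 | 1.38 | −0.38 |

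Two things follow.
- Under the literal rule the scales contradict each other at every d, both as RR and as 1 − RR.
- Literal stigma coding gives a positive efficacy only because the coding and the 1 − RR formula each change the sign. If stigma alone is recoded and 1 − RR is kept, a true benefit appears as −0.16 to −0.38.

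**The case against.** The strongest reply is that no reversal is written. Follow-up minus baseline is the ordinary change score. Direction is fixed when the change is made discrete, and that step is left open. Since the variable is called improvement and the aim is less stigma, coding a fall as improved is compatible with the text. The scoring direction of the stigma scale is also inferred from the protocol's aim and is not stated.

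This stands in part: the miscoding is conditional on a reading. It does not clear the plan, because a variable bound for a binomial model needs a direction and a cut-off, and neither is given.

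A reader might go further and infer that the plan reverses the reported stigma result. The documents do not support that. The quantity the plan reports is 1 − RR, and under literal coding it is positive for stigma when the messages help. The negative figure is the one for QoL.

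A reader might also infer that any one-point change counts as improved, so that about 50% of each arm improves when there is no effect, and that reducing change to its sign keeps only about 64% (2/π) of the information for a small normal shift. Both figures require a cut-off at zero, which the plan does not state.

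Finally, the signed-rank and Mann-Whitney tests use the scores themselves and would not be affected by miscoding. That is correct. However, the first compares participants with their own baseline, the second ignores baseline, and neither comes with a planned effect estimate.

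**Conclusion.** The point holds as an undefined and potentially contradictory derivation. One subtraction serves two outcomes with opposite directions of benefit, with no scoring direction, coding or threshold stated, and it feeds a 1 − RR formula that does not suit a favourable event. On the natural but unstated reading, benefits of 0.2 to 0.5 SD give stigma RRs of 0.84 to 0.62 and QoL RRs of 1.16 to 1.38. The corresponding 1 − RR values are +0.16 to +0.38 for stigma and −0.16 to −0.38 for QoL.

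These sizes rest on the assumed scoring directions, normal change with equal SDs, no mean change in control, and a cut at zero. The conflict in sign does not depend on the particular value of d. The documents do not establish that the stigma result will be reported with the wrong sign. They do leave the sign open for two outcomes named under the primary objective, and this should be settled before the analysis.

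**What to change.** In Section 12.2.2:

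1. State for each scale whether a higher score is better or worse.
2. Make the main between-arm comparison of stigma and QoL the follow-up score adjusted for its baseline score, reported as a difference in score with its confidence interval.
3. If an improved yes/no variable is kept as a secondary display, define it as baseline minus follow-up for stigma and follow-up minus baseline for QoL, on the scoring directions assumed above, each with a stated threshold.
4. For that display, report the RR of improvement directly, or apply 1 − RR only to non-improvement. Items 3 and 4 must be made together, because recoding stigma alone would turn a real benefit into negative efficacy.

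The cost is plan wording only. The baseline and follow-up scores are already scheduled, so no new data are needed. The downside is that the main result is a score difference and not an efficacy percentage. The preference for the baseline-adjusted score is a separate gain over a dichotomised change. The sign problem alone could be cured by items 1, 3 and 4.
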